## 6. Summary

---

Drug product ID	PRO-087
Study drug:	0.1% sodium hyaluronate, free-preservative 0.18% chondroitin sulphate
Therapeutic indication:	Ocular surface lubricant
Protocol ID:	SOPH087-0415/IV
Sponsor:	Laboratorios Sophia, S.A. de C.V.
Version:	2
Date:	February 2016
Study title	Efficacy and Safety of the Ophthalmic Solution PRO-087 versus Systane ® Ultra and Systane ® Ultra Preservative Free on the Tear Film Dysfunction Syndrome from Mild to Moderate  Clinical trial

Main objective	To evaluate the effectiveness of preservative-free ophthalmic formulation PRO-087 (by Laboratorios Sophia, S.A. de C.V.) to restore the anatomical and physiological characteristics of the ocular surface, as well as its distribution and the characteristics of the mild to moderate tear film dysfunction syndrome compared to Systane ® Ultra and Ultra Systane ® preservative free (by Laboratorios Alcon, S.A. de C.V.).
Study design	Controlled, randomized, double-blind, masked clinical study, comparing the safety and efficacy of preservative-free PRO-087 vs Systane Ultra with preservative and Systane Ultra preservative free, in subjects with mild to moderate tear film dysfunction syndrome, for a period of 90 days plus 15 days of remote surveillance, in which one of the three agents will be administered (PRO-087, Systane® Ultra or Systane® Ultra preservative free) with a q.i.d. dosage. in both eyes, with regular follow-up visits (5 overall).
Variables to evaluate	
Best-corrected visual acuity
 
Intraocular pressure
 
Ocular surface
 
Anterior segment examination
 
Posterior segment examination
 
Tear film break-up time
 
Schirmer test
 
Corneal depithelization
 
Goblet cells count
 
Adverse events

Groups	Subjects with a clinical diagnosis of mild to moderate tear film dysfunction syndrome between 18 and 90 years old, without concomitant eye diseases nor requiring different treatments of any of the three interventions in this study They will be randomized in 3 groups where PRO-087, Systane® Ultra o Systane® Ultra preservative free will be administered.

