#### 10.4 Conjunctival Impression Cytology

Impression cytology of the bulbar conjunctiva is a procedure in which the quantity and quality of epithelial cells and component of the ocular surface are evaluated; the primary focus is to evaluate the density and amount of goblet cells in the sample. The observation will take place in the single and specialized center of pathology under digital counting and it will be confirmed by observation.

The procedure consists of the following steps:

1. Tetracaine instillation over the ocular surface
2. Eye speculum placing
3. A minicell will be taken with the mounted Millipore paper.
4. This will be placed manually in contact with the Millipore surface over the nasal bulbar conjunctiva, slightly pressing, without indenting the surface.
5. Cytological fixation spray will be applied (96% alcohol cytospray)
6. This will be placed on a clean and dry bottle to transport it to the sample gathering unit

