5. OSDI
6. Goblet cells population

It is considered that the drug in evaluation PRO-087 is effective for use in patients diagnosed with mild to moderate tear film dysfunction, if they exhibit the changes marked in parameters (14.1.2) by more than 5% of subjects in both eyes, in compliance with all visits and adherence to treatment at an 80% during the time of study assessment.

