#### 14.1.2 Efficacy Assessment Parameters

Parameters	Value
Best-corrected visual acuity	Increase of 1 line in the Snellen chart or 1 logarithmic point (logMAR)
Corneal depithelization	Percentage of the damaged epithelium of the ocular surface, reduction of staining according to the oxford scale.
Tear film break-up time	Increase in the residence of the teal film, measured in seconds. Increase of 30% from baseline or equal or more than 10 sec.
Schirmer test	Increase of more than 30%
Adverse events	Presence of adverse events modifying some of the abovementioned criteria or others, evaluated as serious.
OSDI	Reduction of 20% of the total score from the baseline score.
Goblet cells population	Increase of 20% from baseline

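### Goblet-cell efficacy rests on a 20% rise between two impressions with no stated unit, judged without a comparator; under plausible but assumed measurement error, noise alone could pass the 5%-of-subjects rule

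*Combined protocol and SAP*

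**What the plan says.** The efficacy table in section 14.1.2 sets the goblet-cell criterion as "Increase of 20% from baseline". Sections 9, 11.1 and 11.4 (final visit) schedule impression cytology at baseline and day 90 only, so each eye's result is a ratio of two measurements.

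Section 10.4 says that "the primary focus is to evaluate the density and amount of goblet cells in the sample". The sampling step reads: "This will be placed manually in contact with the Millipore surface over the nasal bulbar conjunctiva, slightly pressing, without indenting the surface". The steps describe one impression and mention no replicate. They give no membrane area, contact time, number of fields, unit or rule for an inadequate sample. Reading takes place in a "single and specialized center of pathology under digital counting and it will be confirmed by observation".

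The variable has other names elsewhere: "Goblet cells count" in the section 6 summary and "Goblet cells population" in section 14.1. Section 14.1 calls PRO-087 effective if the section 14.1.2 changes are shown "by more than 5% of subjects in both eyes, in compliance with all visits" and with 80% adherence. That sentence names no comparator arm. The entry criteria (sections 12.1 and 12.2) set no goblet-cell limit.

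**The concern.** A percentage-change cut on two single measurements is only as good as their repeatability. The number of cells on a membrane depends on how much epithelium the hand-placed impression lifts, and the count carries its own sampling error. If the combined error is not small against 20%, some eyes with no true change will cross the cut.

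That matters because of the rule built on it. The bar is more than 5% of subjects, with no control arm to subtract the background rate. If chance alone produces a rate near or above 5%, passing the rule says nothing about the drug. Goblet cells are one of six efficacy variables and the one quantity that the cytology section singles out, so they bear directly on the before-and-after histological comparison in objective 5.2.3.

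**Working it through.** The plan gives no goblet-cell count, SD, CV or expected response rate, so there is no figure of its own to reproduce.

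**Inputs from the documents.** Cut: day-90/baseline ratio of at least 1.2 (section 14.1.2). Two time points (section 9). Both eyes, more than 5% of subjects (section 14.1). 96 subjects per group, 80 before the allowance for losses (section 13.3).

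**Assumptions, not in the documents.** Mean count per impression m = 25 to 200. Extra sampling CV per impression (pressure, area lifted) c = 10% to 20%. No true change. Independent errors at the two visits. Correlation between the two eyes' errors of 0 or 0.5.

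**One eye.** SD of the log ratio = √(2/m + 2 ln(1 + c²)), and P(response) = 1 − Φ(ln 1.2 / SD), with ln 1.2 = 0.1823.

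- m = 200, c = 10%: SD = √(0.0100 + 0.0199) = 0.173; 0.1823/0.173 = 1.054; P = 14.6%.
- m = 100, c = 20%: SD = √(0.0200 + 0.0784) = 0.314; ratio 0.581; P = 28.1%.
- m = 25, c = 20%: SD = √(0.0800 + 0.0784) = 0.398; ratio 0.458; P = 32.3%.

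Exact count distributions agree closely: 14.8% for the first case and 28.5% for the second.

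**Both eyes.** P² if the eyes are independent; the bivariate normal probability if correlated 0.5.

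**The 5% rule.** 5% of 96 is 4.8, so at least 5 subjects are needed. The chance is the upper binomial tail with n = 96 and the both-eyes probability.

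| Cells, extra CV | One eye | Both eyes, independent | Both eyes, correlation 0.5 | More than 5% of 96, independent | More than 5% of 96, correlation 0.5 |
|---|---|---|---|---|---|
| 200, 10% | 14.6% | 2.1% | 5.5% | 5.5% | 62% |
| 100, 10% | 18.1% | 3.3% | 7.5% | 21% | 86% |
| 100, 20% | 28.1% | 7.9% | 14.2% | 88% | above 99% |
| 25, 20% | 32.3% | 10.5% | 17.5% | 98% | above 99% |
| 25, counting only | 26.0% | 6.7% | – | 78% | – |
| 100, counting only | 9.9% | 1.0% | – | 0.3% | – |
| 200, counting only | 3.4% | 0.1% | – | below 0.1% | – |
| 500, counting only | 0.2% | below 0.1% | – | below 0.1% | – |

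The counting-only rows have no correlated column because pure counting errors in the two eyes are independent. With 80 subjects (5% is 4, so again at least 5 are needed), the independent-eye chance in the first four rows runs from 3% to 93%.

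**Wider range.** If all error is put into one per-measurement CV, the one-eye rate is 0.5% at CV 5%, 9.8% at 10%, 25.8% at 20% and 36.9% at 40%.

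**The case against.** Much of the case on the other side stands.

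- *The size is assumed.* A reader might infer that a one-eye false-response rate of about 15-32% is a property of the plan. It is not: no count, CV or inter-eye correlation appears in the documents, and the plausible range is far wider.
- *The rule works on subjects, not eyes.* Section 14.1 asks for change in both eyes, so the one-eye rate overstates the exposure. The both-eyes figures are the relevant ones.
- *Density is named.* A reader might say that the count has no area basis at all. Section 10.4 names density first, and density implies an area. If density is what is reported, and if dividing by area removed all the extra sampling error, the counting-only rows would apply and the exposure would nearly vanish at 200 or more cells. That is a best case, since area adjustment does not remove variation in impression depth or local patchiness. The text also leaves open whether density or amount is the variable, and over what area.
- *Some noise is already limited.* The site is fixed at the nasal bulbar conjunctiva, and one pathology centre reads the slides by a confirmed digital count. That the impression is single is an inference from the absence of any replicate.
- *The arms share the noise.* A reader might infer a bias towards PRO-087. The documents do not support that: allocation is random, the noise falls on all three arms, and section 15 plans between-group tests. There it dilutes the comparison.
- *Joint reading.* Section 14.1 refers to the changes in the plural and may require all parameters together. On that reading goblet cells alone could not declare efficacy, though this component would still be easy to pass.

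**Conclusion.** The concern holds in a limited form. The goblet-cell criterion is a bare 20% rise on two impressions, in an unspecified unit, fed into a rule with no comparator. Nothing in the plan keeps the background response rate below the 5% bar. With 25-200 cells and 10-20% extra sampling CV, about 2-10% of unchanged subjects (independent eyes) or 6-18% (correlation 0.5) would respond in both eyes. The chance that noise alone exceeds 5% of 96 subjects then ranges from about 5% to above 95%. That spread is the finding: the answer depends on quantities that the plan neither states nor controls. With large counts and no extra sampling error the risk is negligible.

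The documents do not support saying that noise would by itself have PRO-087 declared effective, or that it tilts the randomised comparison. The effect there is lost power. The change is worth making, but the trial does not depend on it: the sample size is driven by the Schirmer test.

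**What to change.** 1. In section 10.4 and the laboratory instructions, define the variable as goblet-cell density: cells per mm² over a stated area of the central digital count, with inadequate samples flagged. Use that one name in sections 6, 14.1 and 14.1.2.
2. In sections 14 and 15, base the goblet-cell conclusion on day-90 log density compared between arms, with baseline log density as covariate. This uses a baseline that is already collected and replaces both the uncontrolled 20%/5% rule and the unadjusted ANOVA for this variable. State how zero counts are handled on the log scale.
3. Keep the 20% responder rate, tabulated by arm, as descriptive only. Requiring the rise also to clear counting-error limits is not advised, because such a rule is hardest on eyes with low counts.
4. Optionally, read slides masked to visit.

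Cost: some laboratory and analysis wording and slightly more analysis work. No extra visit, sample or subject is needed. The sponsor gives up a stand-alone responder claim for goblet cells.

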#### 14.2 Tolerability Evaluation

Tolerability variables of the study drug PRO-087 will be evaluated in the visits indicated in the schedule, using the following parameters:

1. Burning
2. Foreign body sensation

3. Tearing
4. Conjunctival hyperemia
5. Pruritus
6. Photophobia
7. Tear secretion

It is considered that the drug in evaluation PRO-087 is tolerable for use in human beings, if there are no changes on the marked parameters (14.1.2) by more than 5% of subjects, in both eyes, in compliance with all visits and adherence to treatment at an  $\geq 80\%$  during the time of study assessment.

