#### 14.2.1 Tolerability Parameters

Parameters	Value
Burning	It should be recorded as absent on 95% of the evaluated subjects
Foreign body sensation	It should be recorded as absent on 95% of the evaluated subjects
Tearing	It should be recorded as absent on 95% of the evaluated subjects
Secretion	It should be recorded as absent on 95% of the evaluated subjects
Conjunctival hyperemia	
The following must be accomplished:
 
 
• Absent: <math>\geq 95.0\%</math>
 
• Mild: <math>\leq 5.0\%</math>
 
• Moderate: <math>\leq 2.5\%</math>
 
• Serious: <math>\leq 1.0\%</math>
 

Photophobia	
The following must be accomplished:
 
 
• Absent: <math>\geq 95.0\%</math>
 
• Mild: <math>\leq 5.0\%</math>
 
• Moderate: <math>\leq 2.5\%</math>
 
• Serious: <math>\leq 1.0\%</math>
 

Safety variables of the study drug PRO-087 will be evaluated in the visits indicated in the schedule, using the following parameters:

1. Best-corrected visual acuity
2. Intraocular pressure
3. Ocular surface
4. Anterior segment exploration
5. Posterior segment exploration
6. Tear film break-up time
7. Schirmer test
8. Corneal depithelization
9. Adverse events

It is considered that the drug in evaluation PRO-087 is tolerable for use in human beings, if there are not changes on the marked parameters (14.3.1) by more than 5% of subjects, in both eyes, in compliance with all visits and adherence to treatment at an  $\geq 80\%$  during the time of study assessment.

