#### 14.3.1 Safety Parameters

Parameters	Value
Best-corrected visual acuity	No change of 1 line in the Snellen chart or 1 logarithmic point (logMAR)
Intraocular pressure	Measurements below 7 mmHg and over 21 mmHg
Corneal depithelization	Percentage of the damaged epithelium of the ocular surface, reduction of staining according to the Oxford scale.
Anterior segment examination	Abnormalities on any of the comprised structures: Cornea, iris, pupil, iris-corneal angle and crystalline.
Posterior segment examination	Abnormalities on any of the comprised structures: Vitreous, retina, macula and optic nerve.
Tear film break-up time	Reduction of more than 20% over the baseline time.
Schirmer test	Reduction of more than 20%
Adverse events	Presence of adverse events modifying some of the abovementioned criteria or others evaluated as serious.
OSDI	Increase of the score of more than 10 points.

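### Section 14's tolerability and safety verdict rules contain wording errors and gaps that can change the verdict on PRO-087

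*Combined protocol and SAP*

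**What the plan says.** Section 14 gives three verdict rules, each tied to a table and a 5% limit.

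- **Efficacy (14.1):** PRO-087 is effective in patients "if they exhibit the changes marked in parameters (14.1.2) by more than 5% of subjects in both eyes".
- **Tolerability (14.2):** it is tolerable "if there are no changes on the marked parameters (14.1.2) by more than 5% of subjects, in both eyes". The table of tolerability parameters is 14.2.1, whose rows for burning, foreign body sensation, tearing and secretion each read "It should be recorded as absent on 95% of the evaluated subjects". The hyperemia and photophobia rows ask for absence in at least 95% and add limits of 5.0% mild, 2.5% moderate and 1.0% serious. Pruritus is in the 14.2 list but has no row.
- **Safety (text between tables 14.2.1 and 14.3.1):** the drug is again called tolerable, not safe, "if there are not changes on the marked parameters (14.3.1) by more than 5% of subjects, in both eyes, in compliance with all visits" and with at least 80% adherence.

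Two rows of safety table 14.3.1 mirror the efficacy table. The corneal row reads "Percentage of the damaged epithelium of the ocular surface, reduction of staining according to the Oxford scale"; the efficacy row likewise names "reduction of staining according to the oxford scale". The acuity row reads "No change of 1 line in the Snellen chart or 1 logarithmic point (logMAR"), against "Increase of 1 line in the Snellen chart or 1 logarithmic point (logMAR") for efficacy.

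On populations, section 15 also analyses anyone with one post-baseline visit, section 17.4 retains the available data of every withdrawn subject for safety, and section 17.6 sends adherence below 80% to intention to treat.

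**The concern.** These are the only criteria the protocol states for calling PRO-087 tolerable or safe. If a rule points to the wrong table, a row counts improvement as harm, a unit is undefined or the denominator is not settled, two analysts can reach different verdicts from the same data. A rule that counts residual disease symptoms against the drug also mixes lack of complete response with intolerance.

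**Working it through.** **Inputs.** Subjects per group: 80 before and 96 after the allowance for losses (13.3), so 96 − 80 = 16 planned losses. Limits of 5%, 2.5% and 1.0% (14.2, 14.2.1). LogMAR conversion table (Fig. 10.3.1.1). Elimination at TBUT below 5 s (12.2.3). Safety change for TBUT: a fall of more than 20% (14.3.1). Residual symptom rates on PRO-087 are not given, so a range is assumed.

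**Allowed counts.** 0.05 × 80 = 4.0 and 0.05 × 96 = 4.8, so 4 subjects at either size. Moderate hyperemia or photophobia: 0.025 × 80 = 2.0 and 0.025 × 96 = 2.4, so 2. Serious: 0.01 × 80 = 0.80 and 0.01 × 96 = 0.96, so 0.

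**1. Table cited.** Under 14.1, more than 5% of subjects with a 14.1.2 change supports effective. Under 14.2 as printed, more than 5% with a change in the same table defeats tolerable. For any one parameter the two verdicts are then opposites.

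**2. Corneal row.** The other measured rows of 14.3.1 (IOP, TBUT, Schirmer, OSDI) list harms; the corneal row lists a reduction of staining. If 5 of 80 subjects improve, 5/80 = 6.25%, which meets the efficacy rule and fails the safety rule. A worse Oxford grade is not named. Only the general anterior-segment row, which mentions the cornea but sets no grade, could catch it.

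**3. Acuity rows.** In Fig. 10.3.1.1, 20/20 is 0.0 and 20/200 is 1.0, with ten rows of 0.1 between them; higher is worse. If a point means 1.0 logMAR it is ten table rows, and a gain of that size is possible only from −0.3 + 1.0 = 0.7 (20/100) or worse. If it means one row it is 0.1. One metric Snellen line in the same table is 0.1 or 0.2: the steps from 6/60 to 6/3 are 0.2, 0.2, 0.1, 0.2, 0.1, 0.2, 0.1, 0.1, 0.1. The rows say neither which unit is meant nor which direction the number moves. The safety row also puts a no-change criterion inside a rule requiring no changes.

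**4. Symptom rows.** Section 3 lists hyperemia, tearing, photophobia, burning and foreign body sensation as signs and symptoms of the disease. Read as absolute levels, a row passes with probability P(X ≤ 4), X ~ Binomial(n, p):

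| Assumed residual rate p | n = 80 | n = 96 |
|---|---|---|
| 3% | 91% | 84% |
| 5% | 63% | 47% |
| 10% | 9% | 3% |
| 20% | <0.1% | <0.1% |

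For hyperemia and photophobia these are upper bounds, because the row also fails with 3 moderate cases or 1 serious case.

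**5. Verdict population.** Near the limit the choice of set matters: 4/80 = 5.0% passes. Adding one eliminated subject who had the event, with between one and all 16 losses contributing data, gives 5/81 = 6.2% to 5/96 = 5.2%, which fails. Away from the limit it does not: 8/96 = 8.3% fails, and removing 2 or 3 of those subjects still fails (6/94 = 6.4%, 5/93 = 5.4%). For TBUT the exclusion depends on the outcome. Since 0.8 × 6.25 = 5.0, any fall of more than 20% from a baseline of 6.25 s or less ends below 5 s. Seen at day 7, 30 or 60, the safety event is itself a ground for elimination. Inclusion admits baselines above 5 s and below 10 s, so such subjects can enter.

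**The case against.** Much of this can be read charitably. The citation of 14.1.2 looks like transposed digits, and the safety rule's intent is clear from the table it names. A reader might infer that the plan makes efficacy and tolerability mutually exclusive; that follows only from the literal text.

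A reader might also infer that the efficacy acuity criterion runs in the wrong direction, because a rise in logMAR is a loss. The documents do not establish that: the parameter is visual acuity, and an increase can mean that acuity improves. What stands is the undefined unit and sign. The one-line branch would still catch a large loss.

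On symptoms, the 14.2 rule speaks of changes, which may imply a comparison with baseline. The rows are nevertheless absolute levels, so rule and table disagree. It is tempting to say the symptom rows cannot be passed, since section 3 cites a 30 to 50% prevalence, but that figure concerns users of preserved drugs, a different population.

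On populations, a per-protocol verdict can coexist with the intention-to-treat analyses of sections 15 and 17.6. A reader might infer a contradiction with both, but only section 17.4 conflicts directly, and only for safety. What stands elsewhere is that no section says which set governs the verdict.

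**Conclusion.** The point holds and should be fixed. The table citation, the safety conclusion, the missing pruritus row and the corneal row are wording errors; the corneal row is the most consequential, since as printed it penalises improvement and does not name worsening. The acuity criteria are undefined in unit and sign. The symptom rows and their rule must be reconciled: under the absolute reading a modest residual rate makes a pass unlikely (9% or 3% per row at an assumed 10%), but the true rate is not in the documents. The population matters only around 4 versus 5 events, and there it depends partly on the outcome through TBUT elimination. The randomised comparisons in section 15 and the adverse-event reporting in section 18 do not rest on these rules.

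**What to change.** - **References:** cite 14.2.1 in the 14.2 rule, give pruritus a row or delete it, and let the 14.3.1 rule conclude that the drug is safe.
- **Corneal row of 14.3.1:** reword as an increase in Oxford grade, with the size set by the sponsor.
- **Acuity rows:** state both in logMAR with unit and direction, with the size set by the sponsor and reconciled with Fig. 10.3.1.1. Remove the double negative.
- **Symptoms:** count burning, foreign body sensation, tearing and hyperemia as new or worse than baseline. Say how photophobia, secretion and pruritus are judged.
- **Population:** apply the safety verdict to all treated subjects with post-baseline data, including eliminated subjects up to their last visit, in line with section 17.4. State which set governs tolerability. The elimination rule itself is left to the sponsor.
- **Decision rule:** name the visit or visits used, whether one failed row fails the verdict, and whether the both-eyes condition means both assessed or both affected.

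The cost is rewording, with no new visits. Baselines for burning, foreign body sensation, tearing and hyperemia are already scheduled (sections 9 and 9.1). Photophobia, secretion and pruritus are not in the schedule key, and the OSDI light-sensitivity item records frequency rather than the 14.2.1 grades, so a like-for-like baseline would need an added item. Safety counts may look less favourable and tolerability counts more favourable.
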